Developing adaptive interventions for cocaine cessation and relapse prevention; Using event-related potentials to predict treatment outcomes in cocaine use disorder (“Adaptive trial”)

NCT02896712

Version Date: 06/15/2020

Protocol Title:	Developing adaptive interventions for cocaine cessation and relapse prevention; Using event-related potentials to predict treatment outcomes in cocaine use disorder ("Adaptive trial")
Principal Investigator:	[name]
Co-Investigators:	[name], [name], [name], [name], [name], [name], [name], [name]
Study Coordinator:	[name]
Population:	N = 160 adults (18-60 years old) with cocaine use disorder recruited from the Houston metropolitan area
Number of Sites:	Single site
Study Duration:	Four years
Study Duration per subject:	14 weeks, with 3 visits per week for a total of 42 study visits

Project Summary

Drug addiction is a chronic, devastating, but *treatable* disorder, for which there exists a growing armamentarium of evidence-based interventions, including pharmacotherapies and psychotherapies. A core principle of drug addiction treatment, however, states that *no single treatment is appropriate for everyone*; rather, treatments need to be adjusted based on patient characteristics and response in order to be maximally effective. Ideally, clinicians would identify a sequence of interventions that works best across different stages of addiction treatment, from abstinence initiation to relapse prevention. Adaptive treatment interventions have been used successfully to inform this sequential clinical decision-making process. For cocaine use disorders (CUD), the most potent intervention currently available for initiating abstinence is behavior therapy using contingency management (CM) procedures. Intensive CM has been shown to produce initial cocaine abstinence rates of 40%, unmatched by all other forms of behavioral or pharmacological treatment, making it a prototypical first-line therapy for CUD. Importantly, achievement of initial abstinence predicts future abstinence. For the clinician, these research findings translate into a straightforward question: *Can we drive CM response rates even higher with targeted adjunctive interventions?*

The proposed sequential, multiple assignment, randomized trial (SMART) will provide the data needed to answer this question. First, we will determine whether Acceptance and Commitment Therapy (ACT) in combination with CM increases initial treatment response rates. We hypothesize that four weeks of treatment with ACT+CM will produce higher abstinence rates than initial treatment combining standard Drug Counseling with CM (DC+CM). The hypothesized synergism of ACT+CM on primary treatment mechanisms of experiential avoidance and reward sensitivity, respectively, will be examined. Second, for patients who do not respond to initial treatment, we will examine whether dopamine-targeted pharmacotherapy is an effective augmentation strategy. Specifically, we hypothesize that continued ACT+CM treatment with modafinil augmentation will be most effective in promoting abstinence relative to treatment combinations involving continued DC and/or placebo. Third, for patients who respond to initial treatment, we will assess the relative benefit of continued treatment with ACT+CM, as compared to DC+CM, to prevent relapse. ACT emphasizes goal-directed actions based

on values that are intrinsically motivating, and is thereby expected to be a more effective intervention for extending the duration of abstinence following initial treatment with intensive CM.

In summary, results from this Stage II (PA-13-078) project should support a Go/No Go decision about further Phase III, confirmatory studies. The primary aims of this project address an important NIDA research priority and have the potential to significantly impact how we tailor treatment of CUD to maximize outcomes.

Background Information

Cocaine use disorders comprise a public health problem in need of new treatment approaches. Cocaine affects multiple brain circuits, with prolonged exposure compromising cognitive and behavioral processes associated with reward, motivation, learning, and inhibitory control.¹⁻³ The complexity of the disorder has presented treatment challenges. Controlled studies have demonstrated effectiveness for several types of behavioral therapies, including cognitive-behavioral therapy (CBT), motivational interviewing (MI), and CM,^{4,5} along with promising pharmacotherapies.^{6,7} Despite the growing armamentarium of CUD interventions available, the treatment field continues to rely on fixed-intervention models (all patients offered the same type or dosage of intervention) which has fallen short of substantially improving clinical care and outcomes.⁸ Adaptive intervention methodology responds to the call for new behavioral and integrative treatment development research to improve effectiveness by allowing for greater individualization or “tailoring” of treatment to the needs of the individual (PA-13-077; NIDA Principles of Drug Addiction Treatment, 2012).⁹

An adaptive treatment intervention (ATI) for CUD aims to answer the ultimate clinical question -- what sequence of interventions work best for each individual across the stages of addiction treatment, from abstinence initiation to relapse prevention? The sequential multiple assignment trial (SMART) is an experimental design used for constructing empirically-supported ATIs. The first decision stage of the SMART provides data for identifying the best initial treatment. The second decision stage of the SMART compares second treatment options for initial treatment responders/non-responders. We propose a SMART design to find the sequence of integrated therapies that will achieve the best possible outcomes for both responders and non-responders over the course of CUD treatment. The following sections summarize the conceptual framework along with **supporting data** for the hypothesized ATIs, shown below.

[figure not shown]

Figure B.1.2. Hypothesized adaptive treatment interventions using integrated therapies.

CM is an efficacious intervention for initiating abstinence from cocaine. Based on operant learning principles, CM interventions seek to increase availability of reinforcement derived from non-drug alternatives, increase constraints on reinforcement derived from substance use, and deliver these environmental contingencies to accommodate the temporal discounting behavior that is characteristic of substance use disorders.¹⁰ An extensive literature of controlled-studies documents the success of these interventions.¹¹ We¹² and others¹³⁻¹⁵ have implemented high-magnitude CM interventions during initial weeks of CUD treatment to produce abstinence rates as high as 40%. To our knowledge, CM is currently the most reliably effective method for facilitating initial abstinence. Given the robustness of initial abstinence in predicting long-term abstinence, e.g.^{16,17} it behooves practitioners and treatment researchers to find new approaches to increase the number of CM “responders”.

Adding acceptance and mindfulness-based treatment strategies with CM may lead to improved abstinence outcomes. While highly effective, CM response is variable with significant rates of non-response, even to high-magnitude rewards. Little is known about individual-level characteristics associated with CM response, with the exception of intake urine status considered a marker of disorder severity.^{15,18,19} To our knowledge, we reported the first study examining **modifiable** cognitive-affective characteristics associated with CM response.²⁰ Ninety-nine treatment-seeking patients with CUD received 4 weeks of high-magnitude CM-based treatment targeting abstinence initiation.¹² A post-hoc comparison of responders, i.e., those achieving two consecutive weeks of cocaine-negative urine screens, and non-responders was performed on pretreatment measures of negative affect, experiential avoidance, cocaine craving/withdrawal symptoms, and impulsivity. Notably, while the groups reported similar levels of negative affect, impulsivity, and craving/withdrawal, the non-responder subgroup had higher levels of experiential avoidance (EA). In other words, non-responders differed from responders in their approach to handling negative internal experiences (e.g., craving, negative emotions). EA, or the tendency to avoid or respond inflexibly with drug use behaviors when experiencing aversive states, is thought to provide negative reinforcement for continued use despite the availability of competing non-drug rewards. These findings suggest that targeting problems in EA and behavioral flexibility may prove to be effective in enhancing response to CM.

Acceptance and Commitment Therapy (ACT) is a third generation CBT intervention, emphasizing the role of EA and inflexibility as key mechanisms underlying and positively correlated with psychopathology including drug use.^{21,22} ACT uses experiential exercises and metaphors to change the function of distressing thoughts and feelings, essentially helping clients make decisions and choices based on personal goals and values rather than on avoidance or control through substance use.²³ By reducing EA and improving distress tolerance, ACT *may help facilitate sensitivity to, and contact with, non-drug sources of reward made available via CM.*

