Participants. The study will enroll treatment-seeking individuals, 18 to 60 years old, who meet current DSM-5 criteria for CUD of at least moderate severity (≥ 4 symptoms). Eligible subjects must submit at least one positive urine toxicology screen for the cocaine metabolite (BE ≥ 150 ng/mL) during intake; a standard requirement in most cocaine trials to ensure enrollment of patients actively using cocaine. Subjects meeting moderate or severe criteria for substances other than cocaine, marijuana, alcohol, or nicotine will be excluded. Subjects whose alcohol use meets for physiological dependence requiring detoxification or use that makes participation medically unsafe as determined by the medical director will be excluded. Other exclusion criteria will include the presence of significant and unstable psychiatric disorders, including active psychosis, dementia, or other axis I psychiatric or neurological conditions requiring ongoing treatment and/or making study participation unsafe. Individuals with a past psychiatric history but without symptoms reported within the past 12 months prior to assessment, and who meet other inclusion criteria, may be eligible to participate. Individuals having medical conditions (e.g., severe cardiovascular disease, severe liver impairment) or taking medications (e.g., propranolol, phenytoin, warfarin, or diazepam) known to be contraindicated for modafinil pharmacotherapy will be excluded. To be eligible, females of childbearing potential must agree to use an acceptable method of birth control during study participation and for one month after discontinuation of the study medication. Non-hormonal methods of contraception are recommended, including barrier contraceptives (e.g., diaphragm, cervical cap, male condom) or intrauterine device (IUD). Steroid contraceptives if used with non-hormonal methods are acceptable. No pregnant women will be permitted in study. There will be separate inclusion/exclusion criteria for the Electroencephalogram (EEG) sub-study. Individuals with hairstyles that are incompatible with an EEG net (e.g., tight braids, ponytails, wigs, weaves, dreadlocks, or head scarves, etc.) and are unwilling to change the hairstyle will be excluded only from the EEG portion of the study. Individuals will also be excluded if they have a history of epilepsy or seizure disorder or head injury with loss of consciousness in the past 5 years.

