Phase 1 treatments. Consenting subjects will be assigned to one of the two 4-week Phase 1 treatments, ACT+CM or DC+CM, using urn randomization to ensure balance between groups on baseline EA level, coded as "high" if AIS score > 45, or "low"≤ 45. Subjects in both treatments will be scheduled to attend three clinic visits per week (MWF) during the 4-week period. **Two** of these weekly visits will include 1-hour therapy sessions (ACT or DC).

Acceptance and Commitment Therapy-Cocaine Use (ACT). The overarching goal of ACT is to decrease experiential avoidance while increasing acceptance and willingness to experience unpleasant thoughts, feelings, and physical symptoms. More specifically, ACT will assist cocaine patients to notice their internal cravings and triggers, abandon their attempts to manage these triggers via active avoidance, suppression or other control-based strategies, and to make commitments to engage in behaviors consistent with their chosen values or goals. ACT encourages clients to experience thoughts and feelings from an observer perspective, and helps them not to believe distressing thoughts and feelings as if they are literally true and in need of action. ACT treatment will be based on the therapy manual developed and tested previously.^{38, 39} The manual covers 10 core topics listed in **Table B.3.2.vi.** Our experienced ACT therapists will be taught to use the manual as a map with flexibility to "go with the client" so long as issues of acceptance, diffusion, values, and committed action are thoroughly covered. Mindfulness exercises, metaphors, and homework sheets will be used to pursue therapeutic goals, more so than didactic instruction. Masters-level therapists with ACT experience from our previous trial ³⁸ will be trained and supervised by [name] (Co-I) and [name] (Consultant).

Drug Counseling (DC). We will use the manual-guided individual DC modeled after the NIDA Collaborative Cocaine Treatment Study ⁴⁰ and used as the active control therapy in our previous studies.^{38, 41, 42} DC approximates clinical practice as it is considered the most common type of evidence-

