based treatment in the community for patients actively using cocaine. DC educates patients about important concepts in addiction recovery based on the underlying philosophy that physical, emotional, spiritual, and interpersonal needs must all be addressed to support recovery. Accordingly, the DC manual covers the core topics listed in **Table B.3.2.vi**. Masters-level therapists with DC experience from our previous trials^{41, 42} will be trained and supervised by [name] (Co-I).

Contingency Management (CM). We will use the same high-magnitude CM schedule shown previously to be feasible and effective in facilitating initial cocaine abstinence.¹² Subjects will earn vouchers for cocaine-negative urine samples collected at scheduled clinic visits (MWF) each week. Under an escalating reinforcement schedule, voucher values will begin at \$15 and increase by \$10 for each consecutive negative urine. Provision of a cocaine-positive urine or failure to provide a scheduled sample will result in no vouchers earned and will reset the schedule to the initial value (\$15). Bonus vouchers (\$10) will be given for completing all study-related tasks in a given week. Subjects will redeem their earned vouchers for cash loaded to the ClinCard, a reloadable debit card.

Initial response and re-randomization. Following Phase 1 treatment, the primary outcome of response/non-response will be determined. Subjects who submit 6 consecutive (2 weeks) cocaine negative urine samples by week 4 will be classified as responders. Those who fail to meet response criteria will be classified as non-responders.

During second (Phase 2) treatment:

- Responders will continue to receive their assigned initial treatment, as described below.
- Non-responders in each initial treatment arm will be re-randomized to a second treatment consisting of pharmacotherapy augmentation with either modafinil or placebo.

All subjects will attend three clinic visits per week (MWF) during the 8 week second treatment period.

Table B.3.2.vi. 10 Core Topics for ACT and DC

Second (Phase 2) treatments	ACT	DC
Continued ACT or DC. Twice weekly 1-hour ACT and DC sessions will continue during the 8 weeks of second treatment, covering the core topics shown in Table B.3.2.vi.	Preparing to begin	Planning my recovery
	Values	Stages of recovery
	Making contact with the cost of using	People, places, things
	Creative hopelessness	Self-help groups & support systems
	Control v Willingness	Establishing a support system

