exist. Posterior distributions can then be used as informative priors for continued monitoring in expansions of treatments and treatment strategies exhibiting initial promise.

Analytic strategy. Broadly, the analytic strategy will use generalized linear modeling. Continuous, dichotomous and time-to-event data will utilize linear, logistic, and proportional hazards regression respectively. Longitudinal analyses will employ generalized linear mixed models. All of these SAS (ver 9.3) procedures permit Bayesian analyses. Primary analyses will use intention-to-treat principles, with missing observations imputed as positive. Secondary analyses will implement joint modeling of observed outcomes and the missing data which is robust to ignorable missingness.^{81, 82} Sensitivity analyses will evaluate robustness of analytic conclusions to missing data. Non-ignorable missing data patterns will be addressed through pattern-mixture modeling methods.⁸¹ Prior distributions for comparison of proportions will use $\sim \text{Beta}(a = 1, b = 1)$ priors. Linear, logistic and Cox Proportional Hazards regression coefficient priors will take the form $\sim \text{N}(\text{mean} = 0, \text{var} = 1 \times 10^6)$ in the linear, log (odds) and log scales respectively. Level one error variances will be specified as $\sim \text{Inverse Gamma}(\text{shape} = 0.001, \text{scale} = 0.001)$; level two variances will use $\sim \text{Uniform}(0, 1000)$ distributions. Sensitivity analyses using optimistic and pessimistic, skeptical priors will evaluate prior assumptions.^{83, 84} Inverse probability weight will permit unbiased effect size estimates in the context of re-randomization. Finally, coding procedures will permit identification of each salient effect. Specifically, at the initial randomization ACT+CM and DC+CM will be coded as 1 and -1 respectively. For the re-randomization: 1) non-responders receiving continuation therapy will be coded 1 while all other participants will be coded 0; 2) non-responders receiving augmentation will be coded 1 versus 0 for all other participants.

Hypothesis testing.

Hyp. 1. Initial treatment with ACT+CM will produce higher response (abstinence) rates than initial treatment with DC+CM. Logistic regression will evaluate cocaine-abstinence rates at week 4 as a function of treatment assignment.

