Effect	Posterior Probability $Pr(\theta > 0)$	Power to Detect $Pr(\theta > 0)$	Average Point Estimate	Average Interval (95% C.I.) Estimate
Effect of Initial Treatment Hypothesis Test Aim 1: Contrast 1 vs 2*	0.90	0.83	0.20	0.05-0.34
Effect of Second Treatment (Initial non-responders) Hypothesis Test Aim 2				
Contrast 5 vs 6*	0.80	0.81	0.17	0.06-0.27
Contrast 7 vs 8*	0.80	0.81	0.13	0.05-0.21
Contrast 6 vs 8*	0.85	0.80	0.16	0.07-0.25
Effect of Second Treatment (Initial responders) Hypothesis Test Aim 3:				
Contrast 3 vs 4*	0.85	0.80	0.16	0.07-0.25

*Contrast numbers correspond to numbers in black boxes on Figure B.3.2.x.

constitutes sufficient evidence for results from this Stage II project to support a “Go” decision to advance to Phase III confirmatory studies.

Protection of Human Subjects

Selection Criteria

Eligible participants will:

1. be between 18 and 60 years of age
2. meet DSM-5 criteria for current cocaine use disorder of at least moderate severity (≥ 4 symptoms)
3. have at least 1 positive urine BE specimen (≥ 150 ng/mL) during intake
4. be in acceptable health on the basis of interview, medical history and physical exam
5. agree to use an acceptable method of birth control during study participation and for one month after discontinuation of the study medication. Non-hormonal methods of contraception are recommended, including barrier contraceptives (e.g., diaphragm, cervical cap, male condom) or intrauterine device (IUD). Steroid contraceptives if used with non-hormonal methods are acceptable.
6. be able to understand the consent form and provide written informed consent
7. be able to provide the names of at least 2 persons who can generally locate their whereabouts.

Exclusion criteria include:

8. current DSM-5 diagnosis for substance use disorder (of at least moderate severity) other than cocaine, marijuana, alcohol, or nicotine
9. current alcohol use that meets for physiological dependence requiring detoxification or makes participation medically unsafe as determined by the medical director.
10. have a DSM-5 axis I psychiatric disorder or neurological disease or disorder requiring ongoing treatment and/or making study participation unsafe (e.g., psychosis, dementia).
11. significant current suicidal or homicidal ideation
12. medical conditions contraindicating modafinil pharmacotherapy (e.g., major cardiovascular disease, severe liver disease based on Child-Pugh score of B or C, serious kidney problems)

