assistant will conduct this telephone-screening interview. Eligible subjects will be scheduled for an in-person intake visit at the Treatment Research Clinic (TRC), the outpatient research and treatment facility of the UT Department of Psychiatry and Behavioral Sciences, Center for Neurobehavioral Research on Addiction (CNRA). The first intake appointment will begin with the presentation of the informed consent form. The consent form will detail the requirements of study participation (e.g., # of visits, type of data collected, time commitment, etc.).

Subjects will be told that the purpose of the study is to evaluate a strategy for adapting treatments for improving cocaine cessation and relapse prevention outcomes. Information about the treatment components being studied will be explained. This discussion will include details of the different behavior therapies and how CM rewards will be made available during treatment. Subjects will be informed that they will attend thrice weekly clinic sessions. Other information on the consent form will include a full description of study requirements, reimbursement, risks, benefits, alternatives, and the role of the local IRB. All questions will be answered before written consent is requested.

Once written consent is given, eligible participants will also be asked if they are interested in participating in an optional EEG sub-study. These eligible participants will be informed that participation in the sub-study will not affect their treatment or participation in the main study. Interested participants will then be given an additional informed consent form that describes the purpose, reimbursement, risks, benefits, and alternatives specific to the sub-study to review and sign.

All research conducted at the Substance Abuse Research Center requires approval by the Committee for the Protection of Human Subjects (CPHS) of the University of Texas Health Science Center - Houston. The trial will be registered and updated on clinicaltrials.gov.

Protection Against Risk

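### The Hyp. 1 model and the urn leave out pre-randomisation urine BE status, a likely predictor of CM response; the comparison stays valid but gives up some precision and clarity.

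*Combined protocol and SAP*

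**What the plan says.** - **Predictor.** Background Information, in the paragraph on adding acceptance-based strategies to contingency management (CM), says: "Little is known about individual-level characteristics associated with CM response, with the exception of intake urine status considered a marker of disorder severity".
- **Entry.** The Participants paragraph says: "Eligible subjects must submit at least one positive urine toxicology screen for the cocaine metabolite". Selection Criteria item 3 repeats the rule: "have at least 1 positive urine BE specimen (≥ 150 ng/mL) during intake". Neither asks for a positive result at randomisation.
- **Timing.** Recruitment and Informed Consent implies more than one intake appointment: "The first intake appointment will begin with the presentation of the informed consent form". The number of intake urines and the interval to randomisation are not given.
- **Allocation.** Phase 1 treatments assigns patients "using urn randomization to ensure balance between groups on baseline EA level". No other balancing factor is named.
- **Endpoint.** Initial response and re-randomization says: "Subjects who submit 6 consecutive (2 weeks) cocaine negative urine samples by week 4 will be classified as responders".
- **Model.** Hyp. 1 says: "Logistic regression will evaluate cocaine-abstinence rates at week 4 as a function of treatment assignment". Hyp. 1.a adds only an EA-by-treatment term. The sensitivity analyses under Analytic strategy concern missing data and priors.

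**The concern.** The plan singles out urine status at intake as an established correlate of CM response, then uses it in neither the allocation nor the primary model. Because one positive during intake is enough, an entrant may be below or at/above 150 ng/mL at the last sample before treatment. Negatives from the first treatment visit count towards the six needed, so that starting status plausibly affects the chance of being classed a responder.

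Two things are at stake. The first is efficiency: part of the variance of the ACT+CM v DC+CM difference comes from chance differences between arms in starting status, and a prespecified covariate would remove it. The second is interpretation: Aim 1 concerns response to initial treatment, and without response shown by starting status a reader cannot see how far the overall rate reflects patients who entered treatment with a negative sample.

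**Working it through.** **Inputs from the documents.** N = 160; expected response about 40%; predicted difference 20 points (Power); Aim 1 interval 0.05 to 0.34 (Table B.3.2.x).

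**Assumed inputs.** 80 per arm, since the allocation ratio is not stated; share negative at the last pre-randomisation sample, *q*; response gap between negative and positive entrants, *g*, the same in both arms.

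**1. Check the scale against the plan's interval.** With 40% v 60%, the crude variance is (0.40×0.60 + 0.60×0.40)/80 = 0.00600, so SE = 0.0775 and the 95% half-width is 1.96×0.0775 = 0.152. With 30% v 50%, the variance is (0.21 + 0.25)/80 = 0.00575, SE = 0.0758 and half-width 0.149. The plan's half-width is (0.34 − 0.05)/2 = 0.145, which is close. The calculation is therefore on the plan's scale.

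**2. Size of a chance imbalance.** The SD of the between-arm difference in share negative is √(2*q*(1−*q*)/80). For *q* = 0.30 this is √(0.42/80) = 0.0725, about 7 points.

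**3. Its part in the crude SE.** Multiply by the gap: 0.35×0.0725 = 0.0254, about 2.5 points, with variance 0.00064. This is a component of the 0.00600 in step 1, not an addition to it.

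**4. SE after adjustment (40% v 60%).** Subtract that component, which is *g*²×2*q*(1−*q*)/80:

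| *q* | *g* | Component removed | Adjusted SE | Cut from 0.0775 |
|---|---|---|---|---|
| 0.30 | 0.20 | 0.00021 | √0.00579 = 0.0761 | 1.8% |
| 0.30 | 0.35 | 0.00064 | √0.00536 = 0.0732 | 5.5% |
| 0.30 | 0.50 | 0.00131 | √0.00469 = 0.0685 | 11.6% |
| 0.10 | 0.20 | 0.00009 | √0.00591 = 0.0769 | 0.8% |

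The formula slightly flatters adjustment, because it ignores the cost of estimating the gap. Simulated trials at *q* = 0.30 give about 4 to 5% for the 35-point gap, 1 to 2% for the 20-point gap and about 12% for the 50-point gap.

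**5. Plausibility of the top end.** With *q* = 0.30, *g* = 0.50 and a 40% control rate, positive controls respond at 0.40 − 0.30×0.50 = 0.25. Negative ACT+CM patients then respond at 0.25 + 0.50 + 0.20 = 0.95. With a 30% control rate the figure is 0.85. With missing samples counted as positive, that is high, so 12% is an upper end.

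**6. Decision rules over all trials.** Simulation covered *q* from 10% to 40% and *g* from 20 to 50 points. With no true effect, the chance of passing the Go rule (posterior probability of benefit above 0.80) was about 19% unadjusted, near the 20% that vague priors imply. With a true 20-point effect, the chance of exceeding 0.90 was about 0.89 unadjusted and 0.90 to 0.95 adjusted.

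**The case against.** **The unadjusted analysis needs no rescue.** Randomisation makes the expected imbalance zero, and the crude interval already contains the chance variation. This stands. A reader might infer bias, or error beyond the stated SE; steps 3 and 6 show neither. In the same simulations, trials whose imbalance happened to favour ACT+CM by at least 1 SD had a false-Go chance of 24 to 45% unadjusted, against about 20% adjusted. That describes a selected minority of trials, with the top figure from the most extreme inputs. It is a reason to prespecify the covariate, not evidence that the overall error rate is wrong.

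**The variable is not quite the one the Background names.** Every entrant has a positive intake urine, so intake status is range-restricted, and the Participants paragraph says the rule is meant to secure active users. No passage shows that the last sample predicts response within such a group. This stands, and it is why the gap must be treated as unknown.

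**EA was a reasoned choice of balancing factor.** The Background reports higher EA in CM non-responders, and the AIS description says the cutoff separated responders from non-responders. This also stands: the point is to add a covariate, not to replace EA.

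**A negative sample is not abstinence.** A reader might infer that entrants negative at the last sample have already stopped using. One BE result below 150 ng/mL does not show that. Nor are positive entrants shut out: four weeks at three visits give 12 scheduled samples, so a patient positive at the first six can still supply six negatives.

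**Phase 2.** A reader might infer that an imbalance carries into the re-randomised comparison. Non-responders are re-randomised within each initial arm, so modafinil v placebo stays a randomised contrast there. Baseline imbalance can change cell sizes but does not bias that contrast.

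**Conclusion.** The point holds as a modest gain in precision and interpretation. The plan names a correlate of CM response, lets a closely related measure vary among entrants, and uses it in neither allocation nor the Hyp. 1 model. The planned comparison remains valid and unbiased in expectation.

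The likely gain is a standard error about 4 to 5% smaller if 30% of entrants are negative at the last sample and respond 35 points more often. At the same share it runs from about 1 to 2% (20-point gap) to about 12% (50-point gap), and it falls below 1% if only 10% are negative with a 20-point gap. All these figures rest on assumed shares and gaps and on 80 per arm. The omission itself can be read directly from the text.

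**What to change.** 1. Define baseline cocaine status as the last urine BE result before randomisation, <150 v ≥150 ng/mL. Every entrant has at least one intake result, so the variable can be defined for all. The intake urine testing sits in a separate evaluation protocol, so confirm that the dated results are available to this trial.
2. Add this status as a prespecified main effect in the Hyp. 1 logistic model, with the vague coefficient prior already given under Analytic strategy.
3. Report the risk difference standardised over the status, and compute the posterior probability of benefit on that quantity. This keeps the result on the scale of the planned 20-point difference; the covariate-adjusted odds ratio alone would not.
4. Tabulate Hyp. 1 response by arm and baseline status.
5. Optionally, add the status as a second urn factor for patients not yet randomised. The covariate serves for everyone else.

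The cost is one covariate and one table, plus a change to the urn program if step 5 is taken. The change should be dated before outcomes are compared by arm, since a covariate chosen after an imbalance is seen is open to challenge. If few entrants are negative at that sample, the gain will be slight.
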